### 14.5. Primary Analysis

#### Visual Acuity (logMAR)

Distance monocular high luminance high contrast visual acuity data will be dichotomized into two groups where  $Y=1$  if subjects VA is below 0.176 logMAR and  $Y=0$  otherwise;  $Y$  will be analyzed using a generalized linear mixed model with the logit as the link function. Sequence of lens wear, study period and lens type will be included in the model as fixed effects. Other characteristics such as age may be included as covariates in the model. Site will be included as a random effect (G-side). The covariance between residual errors from the same subject and eye across study periods will be modeled using either homogenous compound symmetry (CS) or unstructured (UN). The structure that returns the lowest finite-sample corrected Akaike's Information criterion will be selected as the structure that best fits the model. The Kenward and Roger method, will be used for the denominator degrees of freedom. The proportion of eye with 0.176 logMAR or better while wearing the Test lens will be estimated using a 95% confidence interval for the estimated proportion.

The null and alternative hypothesis to test for superiority of the Test relative to the pre-defined threshold 0.176 logMAR is as follows:

$$H_o: P_{Test} \leq 90\%$$
$$H_A: P_{Test} > 90\%$$

Superiority will be declared if the lower limit of the 95% confidence for the estimated proportion of eyes with distance monocular high luminance high contrast VA better than 0.176 logMAR while wearing the Test lens is above 90%. i.e.  $P(p_{Test} > 90\%) \geq 0.975$ .

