### 2.2. Endpoints

Primary endpoint

Visual Acuity (logMAR)

Multiple assessments of monocular visual acuity will be made during the study, but the measurements made at post lens fitting using high contrast letters in bright illuminance conditions at distance (4 meters) will be the primary endpoint. VA will be assessed using ETDRS Charts. Additionally, visual acuity will be measured using high and low contrast charts in bright illuminance conditions. Visual acuity will also be measured using normal illumination and normal contrast charts, while wearing goggles. See [REDACTED] and [REDACTED] in Appendix E for details regarding the collection of visual acuity (logMAR).

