**Clinical Study Protocol**  
**Johnson & Johnson Vision Care, Inc.**

1.23	Distance ETDRS LogMAR Visual Acuity	
Per [REDACTED], please confirm room illuminance and chart luminance acceptable ranges for both high/low contrast visual acuity testing.
 
 
1. Under high illumination and high chart luminance, record the distance (4 meter) ETDRS high contrast visual acuity twice OD (HC1-HC2) and twice OS (HC3-HC4).
 
2. Under high illumination and high chart luminance, record the distance (4 meter) ETDRS low contrast visual acuity twice OD (LC1-LC2) and twice OS (LC3-LC4).
 
3. With the goggles on, under normal illumination and chart luminance, record the distance (4 meter) ETDRS high contrast visual acuity twice OD (HC5-HC6 and twice OS (HC7-HC8). Allow subject to adjust to dim condition for 3 minutes.
 
 
Letter-by-letter results will be recorded into the electronic data capture form, which will calculate the visual performance score for each chart read.
	[REDACTED]
1.24	Subject Reported Ocular Symptoms	Subjects will respond to a verbal open-ended symptoms questionnaire.	[REDACTED]
1.25	CLUE Post-Fit Questionnaire	The subject will respond to the CLUE Post-Fit Questionnaire	[REDACTED] Appendix A
1.26	Cosmetic Lens Fit Assessment (without slit-lamp)	The Cosmetic Lens Assessment will be assessed by the investigator (without slit-lamp) in primary gaze and extreme gaze (right, left, and upgaze) at a normal conversation distance (approximately three (3) feet away from the subject).	Appendix D
1.27	Hula Hoop Assessment (without slit-lamp) *If unacceptable cosmetic fit in any gaze.*	If there is an unacceptable cosmetic fit in any gaze, the Hula Hoop Assessment will be assessed by the investigator (without slit-lamp) in primary gaze and extreme gaze (right, left, and upgaze) at a normal conversation distance (approximately three (3) feet away from the subject).	Appendix D

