#### 14.2. Sample Size Justification

Approximately 50 eligible subjects will be enrolled to target approximately 40 subjects to complete the study. The sample size was calculated to test both the primary hypothesis with a 2-sided type I error of 5% and a minimum of power of 80%.

Based on historical data from [REDACTED] where the same Test lens was utilized, the proportion of eye at lens fitting for distance monocular high luminance high contrast was 0.995 and the correlation between the left and right eyes was 0.627. Using this information the total number of subjects needed to achieve the primary hypothesis is 34 subjects. To account for subject dropout this study will target to enroll approximately 50 subjects with the aim to complete approximately 40 subjects.

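### The primary logit model has no finite Test-lens estimate in about 98% of trials at the planned 0.995 success rate, and no fallback is stated

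*Combined protocol and SAP*

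**What the plan says.** Section 2.2 sets the primary endpoint as "the measurements made at post lens fitting using high contrast letters in bright illuminance conditions". Section 14.5 dichotomises this acuity at 0.176 logMAR, and the result "will be analyzed using a generalized linear mixed model with the logit as the link function". The same section states: "Sequence of lens wear, study period and lens type will be included in the model as fixed effects". Site is a random effect, the residual covariance is compound symmetric or unstructured (chosen by corrected AIC), degrees of freedom are Kenward-Roger, and age may be added. The decision rule is: "Superiority will be declared if the lower limit of the 95% confidence for the estimated proportion of eyes" exceeds 90%.

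Section 14.2 sizes the trial on historical data in which "the proportion of eye at lens fitting for distance monocular high luminance high contrast was 0.995". It takes a between-eye correlation of 0.627 from the same data, and it aims for about 40 completers from about 50 enrolled.

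Section 14.5 says nothing about zero failures, separation or non-convergence, and names no analysis set. Section 14.9 covers missing data only. Section 14.10 says only that a change of method will be documented and justified in the report. Steps 1.23 and 3.11 take two high-contrast readings per eye, and no section says how they form one binary result.

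**The concern.** A logit model needs failures as well as successes to estimate a proportion. At 0.995 the trial expects fewer than one failing Test eye, and the model splits the Test data into two cells that each need at least one. If either has none, the likelihood has no maximum, and the printed limit depends on where the software stops.

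Section 14.6 lists no secondary analysis, so this is the trial's only confirmatory test. A lens that performs as expected could be reported as passing or failing for numerical reasons, or on a method picked once the failure count is known.

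The unnamed analysis set adds to this. Steps 1.31 and 3.19 stop subjects whose acuity is worse than 20/30 just after the endpoint is measured, and the Per-Protocol Population requires all visits to be completed. A Per-Protocol primary analysis could drop the very failures being counted.

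**Working it through.** **Inputs.** From Section 14.2: rate 0.995, correlation ρ = 0.627, 40 completers, about 50 enrolled. From Section 5.1: two sequences, randomised in blocks of 2, hence 20 subjects and 40 eyes per cell. From Section 14.5: null value 90%, lower 95% limit. Assumed: one binary result per eye, equal sequences, complete data, and 0.627 applying to the pass/fail result (Section 14.2 does not say so).

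**The plan's 34 subjects.** Section 14.2 does not name the test. A two-sided 5% z test of 0.995 against 0.90 with 80% power needs 46.43 eyes, and 46.43 × 1.627/2 = 37.8, so 38 subjects. An exact binomial test with 34 × 2/1.627, about 41 effective eyes, has power 0.995^41 = 81.4%. So 34 is not reproduced by the z test but is not contradicted by the exact one. Nothing below depends on it.

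**Step 1: expected failures.** 80 × 0.005 = 0.4 failing Test eyes.

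**Step 2: saturation.** Intercept, sequence, period and lens have rank 4 over the four sequence-by-period cells. The Test mean is the average of two cell logits, and it is infinite if either cell has no failing eye.

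**Step 3: how often.** P(both eyes of a subject pass) = p² + ρp(1−p) = 0.990025 + 0.003119 = 0.99314. P(no failing eye in a cell) = 0.99314^20 = 0.8715. P(no finite estimate) = 1 − (1 − 0.8715)² = 0.9835. A simulation of 2 million trials also gave 98.35%.

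| True rate | No finite estimate, 40 subjects |
|---|---|
| 0.995 | 98.3% |
| 0.99 | 94% |
| 0.98 | 82% |
| 0.95 | 43% |
| 0.90 | 11% |

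At 0.995 it is 98.8% with 34 subjects and 97.5% with 50. With 40 subjects it is 96.7% at correlation 0 and 99.1% at correlation 1. If both readings entered as independent outcomes it is 94.2% (eyes correlated) or 89.1% (everything independent). Over 34 to 50 subjects and correlations 0 to 1, the ranges are about 60% to 92% at 0.98 and 15% to 66% at 0.95.

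**Step 4: other model terms do not help.** With complete data, marginal estimating equations set each fitted cell proportion to the observed one under either covariance structure. With a random site effect, each passing eye's likelihood keeps rising in its own cell logit. As a check, assume 4 sites, 40 subjects, one failing eye in each of three cells and none in one Test cell. The profile log-likelihood at that cell's logit of 4, 6, 8, 12 and 16 is −14.755, −14.128, −14.042, −14.0291 and −14.0288, so there is no maximum. In a plain binomial logit fit with both Test cells at 40/40, the Wald lower limit is 0.953 after 5 iterations, 0.002 after 8 and 0.000 after 12. That fit illustrates the mechanism and is not the planned SAS output.

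**Step 5: does the replacement matter?** Exact lower limits with 80 Test eyes, 80/1.627 = 49.17:

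| Failing eyes | Clustering ignored | Eyes and failures ÷ 1.627 | Only eyes ÷ 1.627 |
|---|---|---|---|
| 0 | 0.955 | 0.928 | 0.928 |
| 1 | 0.932 | 0.905 | 0.892 |
| 2 | 0.913 | 0.884 | 0.861 |

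At the planning values, P(0, 1, 2 failing Test eyes) = 0.759, 0.114, 0.104. One or two occur in 0.114 + 0.104 = 22% of trials, and there the methods disagree about 0.90.

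**Step 6: analysis set.** At a true rate of 0.90, 1 − (0.81 + 0.627 × 0.09) = 13.4% of subjects have a failing Test eye. Take the limit in the middle column, without the cap described in the fix. On all fitted subjects the lens passes in 1.3% of trials (40 fitted) or 1.2% (50 fitted). On completers only it passes in about 10% or 15% if half of those subjects are stopped, and in over 99% if all are.

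**The case against.** The 98% counts trials with a non-finite logit, not trials whose conclusion is in doubt. With no failing Test eye (76% of trials) every exact limit above passes, and with one failing eye two of the three still do. This is fair: the verdict turns on the later choice of method in about 22% of trials at the planning values. It does not rescue the plan, because the rule in Section 14.5 uses the model's own limit, and that limit does not exist in the other cases either.

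The 82% and 43% figures depend on trial size and correlation, and what SAS would print is unknown. Both points stand. Only the figure at 0.995 is robust, and the case rests on the missing maximum rather than on any printed value.

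The analysis set can be called a separate matter. An ITT set is defined, Section 14.1 says available results are used, and no text plans a completers-only primary analysis. The over-99% figure is an upper bound, since steps 1.31 and 3.19 do not say whether Snellen or ETDRS acuity applies. Even so, Section 14.5 names no set, and a replacement test has to be applied to one.

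The example rule below uses a fixed correlation, non-integer scaled counts and a cap. It is one option among several, and penalised alternatives were not compared.

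**Conclusion.** The concern holds. At the plan's own planning values the primary model gives no valid decision limit in about 98% of trials, and in at least 89% under every correlation and reading assumption examined with 40 subjects. Saturation makes this worse but is not the only cause: with lens as the sole fixed effect, the estimate still fails whenever no Test eye fails, which is 76% of trials at 0.995. The expression in Section 14.5 that resembles a posterior probability comes with no prior, so it is not a usable alternative. This must be fixed before the data are seen. The analysis is wrong as written for the outcome the trial expects.

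**What to change.** In Section 14.5, pre-specify one primary test that is defined with zero or few failures, or make it mandatory whenever either Test cell has no failing eye or the model does not converge. Keep the mixed model as supportive. Apply the test to every subject fitted with the Test lens who has a fitting acuity, not only to completers or Per-Protocol subjects. State how the two readings per eye form one binary result.

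One option: lower limit = 2.5th percentile of Beta(N − X, X + 1), with N = (Test eyes)/1.627 and X = (failing Test eyes)/1.627, so both are divided by 1 + 0.627. Add a cap: never pass with more than one failing eye. With 40 subjects this allows at most one failing eye, with one-sided error 1.3% and power 87%.

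Costs and limits of this option:

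- Only SAP wording changes. Sequence and period adjustment is lost, and the rule relies on one historical correlation.
- With the cap, one-sided error is at most 2.2% for 38 to 50 subjects at any true correlation from 0 to 1, and power at 0.627 is 84% to 88%.
- The cap acts only at 47 to 50 subjects, a likely range if all fitted subjects are analysed. Without it, power there is about 97%, but at correlation 1 the error is 4.4% at 47 and 3.4% at 50. With it, error at 50 is 0.4% at correlation 0.627.
- At 34 to 37 subjects only zero failing eyes pass. Power is 78% to 79%, below the stated 80%, and error at 34 reaches 2.8% if the correlation is 1.

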### 2.3. Hypotheses

#### Primary Hypothesis

1. The proportion of eyes with corrected distance monocular visual acuity 0.176 logMAR or better (ie, Snellen VA 20/30 or better) using the Test lenses under high illumination/high contrast is superior to 90%.

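### Section 14.5 does not say how the Test-lens proportion is taken from the logit mixed model; the usual back-transformed mean lies at or above the proportion of eyes named in the hypothesis

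*Combined protocol and SAP*

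**What the plan says.** The primary hypothesis in section 2.3 concerns "The proportion of eyes with corrected distance monocular visual acuity 0.176 logMAR or better", and claims that this proportion "using the Test lenses under high illumination/high contrast is superior to 90" per cent.

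Section 14.5 dichotomises the acuity result, which "will be analyzed using a generalized linear mixed model with the logit as the link function". It then specifies:

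- Fixed effects: "Sequence of lens wear, study period and lens type will be included in the model as fixed effects".
- Covariates: "Other characteristics such as age may be included as covariates in the model".
- Site: "Site will be included as a random effect (G-side".
- Subject and eye, on the residual side: "The covariance between residual errors from the same subject and eye across study periods will be modeled", with a compound symmetry or unstructured form.
- Kenward-Roger, which "will be used for the denominator degrees of freedom".

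Superiority is declared if the lower 95% limit for the estimated Test-lens proportion is above 90%. The section gives no back-transformation rule, no weights for the two Test cells, no covariate values and no treatment of the site effect in forming that proportion. Section 4.3 says that the study has several sites. Neither the number of sites nor a site variance is given anywhere.

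**The concern.** The hypothesis is about a share of eyes. A logit model with a random site effect does not deliver that share directly. Its usual Test-lens summary differs from it in three ways:

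- It is evaluated at a site whose effect is zero.
- It averages the two Test cells (period 1 of Test/Control and period 2 of Control/Test) as log-odds before back-transforming.
- It is evaluated at chosen values of any covariate that is added.

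The inverse logit is concave above 50%, so each of the first two steps gives a figure equal to or higher than the plain average. Evaluation at a covariate mean acts in the same direction. The trial could therefore report a Test-lens proportion above the share of eyes that passed, and test it against 90%. The optional covariates also leave a single-lens confirmatory estimate open to model choice after the data are seen.

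**Working it through.** **Inputs.** The bar is 90% (section 2.3). The planning proportion is 0.995 and the between-eye correlation 0.627 (section 14.2). About 40 subjects are to complete, so I take 20 per sequence and 40 Test eyes per cell. Site SDs on the logit scale are assumed over a range, because the documents give none. The plan states no figure for this point that could be reproduced, and the stated sample size does not enter.

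**Step 1: site term.** Let η be the logit at a site with zero effect and s the site SD. The population proportion is the average of expit(η + s·u) over a standard normal u, found here by Gauss-Hermite quadrature.

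| Site SD (assumed) | Eyes passing if typical site is 90.0% | Gap (points) | Typical-site value if exactly 90% of eyes pass |
|---|---|---|---|
| 0 | 90.0% | 0 | 90.0% |
| 0.25 | 89.8% | 0.2 | 90.2% |
| 0.5 | 89.1% | 0.9 | 90.9% |
| 0.75 | 88.0% | 2.0 | 91.8% |
| 1.0 | 86.6% | 3.4 | 92.9% |
| 1.5 | 83.2% | 6.8 | 95.0% |

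At the planning value, a typical-site 99.5% corresponds to 99.4% of eyes at SD 0.5 and 99.2% at SD 1.0, a gap of about 0.1 and 0.3 point.

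**Step 2: cell averaging.** Intercept, sequence, period and lens type use four parameters for four cells, so the Test mean is the mean of the two Test-cell logits. No site variance is needed for a gap to appear.

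- Failures 1/40 and 5/40: observed (39 + 35)/80 = 92.5%. Logits ln(39) = 3.664 and ln(7) = 1.946, mean 2.805, expit = 94.3%.
- Failures 1/40 and 7/40: observed (39 + 33)/80 = 90.0%. Logits 3.664 and ln(33/7) = 1.551, mean 2.607, expit = 93.1%.

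If the two cells have equal pass rates, the gap is zero.

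**Step 3: would those examples pass?** With f1 and f2 failures, the SE of the mean logit is ½√(1/f1 + 1/(40−f1) + 1/f2 + 1/(40−f2)).

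- 1 and 5 failures: ½√(1.0256 + 0.2286) = 0.560. Lower limit expit(2.805 − 1.96 × 0.560) = 84.6%. With the SE multiplied by √1.627 (0.714), it is 80.3%.
- 1 and 7 failures: ½√(1.0256 + 0.1732) = 0.547. Lower limit 82.3%, or 77.5% with the same inflation (SE 0.698).

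Both fall well short of 90%.

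**Step 4: fitted check.** An intercept-only pseudo-likelihood model with a random site effect and within-subject residual correlation was fitted to simulated data: 40 subjects with two eyes, 4 or 8 equal sites (assumed), true proportion 90% or 95%, site SD 0, 0.5 or 1.0, 60 data sets per setting. The typical-site estimate was never below the observed proportion. Its mean excess was 0.7 to 2.0 points across settings. Site SD was estimated as about zero in 22% to 63% of fits, where the site-related excess vanishes.

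**The case against.** Four points on the other side carry weight.

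1. **The plan does not name a back-transformed mean.** It refers only to an estimated proportion, so that reading is an inference from the logit link and the Kenward-Roger choice. It is a strong one, as this is what the model ordinarily returns, but what the documents establish is that the derivation is left open.

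2. **The gap is conditional.** It is zero if site variance is zero, or estimated as zero, and there are no sequence, period or covariate effects. Subject and eye correlation is on the residual side, so the largest source of clustering adds nothing to it.

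3. **A reader might infer inflated false superiority claims; that is not shown.** The rule uses the lower limit, and both examples in Step 3 fail clearly. A simplified version of the planned fit was simulated at a true 90% of eyes: 5 sites of 8 subjects (assumed), correlation 0.627, sites minus 1 degrees of freedom when site variance was positive, 4,000 trials per SD. No trial with a failed eye passed at SD 0, 0.5 or 1.0. Trials in which every eye passed were at most 1.65%, below the nominal 2.5% even if counted as successes. Full Kenward-Roger was not run. For the same reason, a firm statement that the degrees of freedom fall to sites minus 1 is not supported.

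4. **A reader might conclude that site has no role in a one-lens test and can be dropped.** It does affect the variance of a single-lens proportion. In the same setting, a subject-clustered logit interval that ignored site wrongly passed 3.1%, 3.7% and 6.8% of trials at SD 0, 0.5 and 1.0. An effective-sample-size Wilson interval passed 1.3%, 1.9% and 4.3%. At SD 1.0 the true standard error is about 34% larger than one that ignores site.

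These points limit the size of the problem and shape the remedy. They do not close the gap between the quantity hypothesised and the one that the model usually yields.

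**Conclusion.** The point holds as a mismatch of quantities combined with an unstated derivation. On the usual reading of section 14.5, the figure compared with 90% is at or above the population proportion of eyes in section 2.3 whenever pass rates exceed 50%. Near 90%, the site term contributes about 1 point at SD 0.5 and about 3 points at SD 1.0. Logit-scale averaging adds to this only if the two Test cells differ. At the planned 99.5%, the site contribution is at most about 0.3 point for SDs up to 1.0, so the choice matters mainly when results fall close to the bar. These sizes rest on assumed site SDs and on the inverse-link mean being the output used. The change is worth making because it is cheap and makes the tested number the hypothesised one. It is not needed to repair a demonstrated error rate.

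**What to change.** State in section 14.5 that the Test proportion is the population-averaged proportion of Test-lens eyes at 0.176 logMAR or better, and put the 95% interval on that quantity. Two routes would serve:

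- Keep the mixed model and standardise its predicted probabilities over the observed sites, sequences and periods.
- Use a marginal model, or a direct proportion, on Test-lens records with clustering by subject.

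Remove the discretionary covariates from the confirmatory estimate. Do not simply drop site: let between-site variation enter the interval, or pre-specify a site-clustered interval as a sensitivity analysis, because an interval clustered on subject alone is too narrow if sites differ materially.

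The cost is a few sentences of plan wording, slightly more programming and, if site variation is carried through, a somewhat wider interval.

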## 4. STUDY DESIGN AND RATIONALE

### 4.1. Description of Study Design

This is a 4-visit, bilateral, dispensing, randomized, double-masked, 2×2 crossover trial. A total of approximately 50 subjects will be enrolled with a target of 40 subjects to complete the study.

The study begins with an initial visit (Visit 1). If a subject is found to meet all eligibility criteria, they will be randomized to one of two lens wear sequences (Test/Control or Control/Test) in a bilateral fashion.

If the subject is dispensed study lenses at the initial visit, three additional visits will be conducted. Subjects will return for their first follow-up visit (Visit 2) approximately 1-week after the initial visit. After Visit 2, subjects will undergo a washout period between 2 to 5 days, where subjects will be instructed to wear their habitual contact lenses. After the washout period subjects will return for Visit 3, where they will be dispensed their second study lens per the randomization schedule. Subjects will return for their first follow-up for visit, their second study lens and final evaluation (Visit 4) approximately 1-week after Visit 3.

Subjects will be advised to wear the study lenses at least six (6) hours per day during the 5-7 day dispensing periods.

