# Clinical Study Protocol

## Johnson & Johnson Vision Care, Inc.

same subject across study periods will be modeled using either homogenous compound symmetry (CS) or unstructured (UN). The structure that returns the lowest finite-sample corrected Akaike's Information criterion will be selected as the structure that best fits the model. The Kenward and Roger method, will be used for the denominator degrees of freedom.

Comparisons between the Test and Control will be carried out using 2-sided 95% confidence intervals constructed for the least-square means (Test minus Control) at the 1-week follow-up evaluation. The null and alternative hypothesis for CLUE vision scores to test for non-inferiority of the Test lens relative to the Control lens is as follows:

$$H_0: \mu_{Test} - \mu_{Control} \leq -5$$
$$H_A: \mu_{Test} - \mu_{Control} > -5$$

Non-inferiority will be declared if the lower limit of the 95% confidence interval for the least-square mean difference is greater than -5. i.e.  $P(\mu_{Test} - \mu_{Control} > -5) \geq 0.975$ .

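### Read literally, section 14.5 treats a subject's two eyes as independent given site, so the standard error for the Test proportion would be too small

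*Combined protocol and SAP*

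**What the plan says.** The primary hypothesis in section 2.3 is about eyes: "The proportion of eyes with corrected distance monocular visual acuity 0.176 logMAR or better" with the Test lens is to exceed 90%. Under section 4.1, eligible subjects enter a crossover in which "they will be randomized to one of two lens wear sequences (Test/Control or Control/Test) in a bilateral fashion", so both eyes wear Test in the same period. At each fitting (section 7.2, steps 1.23 and 3.11) the site records "ETDRS high contrast visual acuity twice OD (HC1-HC2) and twice OS (HC3-HC4"), so every subject contributes a right and a left eye.

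The model in section 14.5 has fixed effects for sequence, period and lens type, a random effect for site, and this residual structure: "The covariance between residual errors from the same subject and eye across study periods will be modeled", as compound symmetry or unstructured. It names no subject effect, no covariance between right and left eyes, and no robust variance.

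The CLUE model in section 14.7 describes its block differently: "same subject across study periods will be modeled using either homogenous compound symmetry (CS) or unstructured (UN"). Section 14.2 gives two planning values. For fellow eyes, "the correlation between the left and right eyes was 0.627"; it does not say whether that correlation is between pass/fail results or between logMAR scores. For the Test lens, "the proportion of eye at lens fitting for distance monocular high luminance high contrast was 0.995".

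**The concern.** The words *and eye* make the natural block one eye of one subject, holding its Test and Control records. On that reading nothing except site links the two eyes of a subject.

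Each eye wears Test in one period only. The covariance that 14.5 does specify therefore joins a Test record to a Control record, and does little for the precision of the Test proportion. The covariance that matters is the one between two Test records from the same subject, and it is not there. If fellow eyes tend to pass or fail together, 80 eyes from 40 subjects carry less information than 80 independent eyes. The lower confidence limit that decides the only confirmatory test would then sit too high.

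**Working it through.** **Inputs.** Null proportion 0.90 (2.3, 14.5). Planning proportion 0.995, left-right correlation 0.627, two-sided 5% error, power at least 80%, 34 subjects needed, about 40 completers of about 50 enrolled (14.2). Decision rule: lower 95% limit above 90% (14.5).

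**The plan's own figure.** With design effect 1 + 0.627 = 1.627 and two eyes per subject, subjects = eyes × 1.627 / 2. At two-sided 5% and 80% power, the normal approximation needs 46.43 eyes, or 38 subjects; the exact binomial needs 36 eyes, or 30 subjects; the arcsine method needs 31.15 eyes, or 26 subjects. None gives 34 exactly. However, 34 subjects are 68 / 1.627 = 41.8 effective eyes, and the exact binomial at 41 to 42 eyes has 81% power, against 95% if all 68 eyes were independent. So 34 is compatible with a calculation that counted the eye correlation, and it is not challenged here.

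**Standard error, large samples.** For N subjects with both eyes on Test and pass/fail correlation φ, the variance of the Test proportion is p(1 − p)(1 + φ) / 2N. Treating eyes as independent gives p(1 − p) / 2N. The ratio of standard errors is 1 / √(1 + φ).

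- If 0.627 is the pass/fail correlation: 1 / √1.627 = 0.784, too small by 21.6%.
- If 0.627 is a logMAR correlation, I assume bivariate normal scores cut at the failing threshold. At p = 0.90 the chance that both eyes fail is 0.0410, so φ = (0.0410 − 0.0100) / 0.09 = 0.344. The ratio is 0.862, too small by 13.8%.
- On the same assumption at p = 0.995, φ = 0.166. The ratio is 0.926, too small by 7.4%.

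**Error rate in a stand-in.** This is not the 14.5 model. It pools Test eyes, takes one result per eye, and uses a Clopper-Pearson limit that treats eyes as independent. With 40 subjects the lower limits for 0, 1, 2 and 3 failing eyes of 80 are 0.955, 0.932, 0.913 and 0.894, so the rule passes with at most 2 failures. The true distribution of failures comes from subjects with

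- P(both pass) = p² + φp(1 − p)
- P(both fail) = (1 − p)² + φp(1 − p)

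At p = 0.90 and φ = 0.627 these are 0.81 + 0.0564 = 0.8664 and 0.01 + 0.0564 = 0.0664, leaving 0.0671 for exactly one failing eye. Over 40 subjects:

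- no failure: 0.8664^40 = 0.0032
- one failure: 40 × 0.0671 × 0.8664^39 = 0.0100
- two failures: 40 × 0.0664 × 0.8664^39 + 780 × 0.0671² × 0.8664^38 = 0.0250

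The sum is 3.8%. With 50 subjects the rule passes with at most 4 failing eyes of 100. One-sided error at p = 0.90, against 2.5%:

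| Subjects | φ = 0.627 | φ = 0.344 | φ = 0 |
|---|---|---|---|
| 40 | 3.8% | 2.3% | 1.1% |
| 50 | 6.3% | 4.4% | 2.4% |

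At φ = 0.344 the error is 3.1% with 38 subjects and 3.4% with 45. The endpoint is measured at fitting, so the number analysed may exceed the 40 expected completers.

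**The case against.** **The block may be meant at subject level.** The phrase in 14.5 could loosely cover all records of a subject, both eyes and both periods. CLUE gives one score per subject, so its wording had no reason to mention eyes. Section 14.2 also shows that the sponsor knew of the fellow-eye correlation. This stands as a possible reading, and nobody should infer that the sponsor decided to ignore the correlation. But the text does not say it, and an analyst following the sentence as written would separate the eyes.

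**The error rates are not from the planned model.** Correct. They show direction and rough size only; inflation of the full 14.5 analysis at this sample size is not shown. With exactly 40 subjects and a logMAR correlation the stand-in error is 2.3%, below nominal. That does not extend to 38, 45 or 50 subjects.

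**The largest figures need 0.627 to be a pass/fail correlation.** Also correct, and the documents do not settle it, so both scales are given.

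**A stronger reading to avoid.** A reader might infer that the two readings give opposite answers to the primary test. In a pooled Test-only analysis of 40 subjects where the only two failing eyes belong to one subject, the independent-eyes lower limit is 0.906 (logit-Wald) or 0.913 (Clopper-Pearson), and a subject-clustered one is 0.830. That does not carry over to 14.5 if the Test proportion is the least-squares mean for lens type. Sequence, period and lens type saturate the four sequence-by-period cells. One failing subject leaves the other sequence group with no failing Test eye, and the logit estimate is then not finite under either reading. The non-finite estimate is a separate matter and is not part of this point.

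**Conclusion.** The concern holds as a defect in the written specification of the only confirmatory analysis. Followed literally, 14.5 leaves out the dependence that governs the precision of the Test proportion. The large-sample understatement of the standard error is about 22% on the pass/fail scale, or 7% to 14% on the logMAR scale under bivariate normality, taking the planning correlation as true. The stand-in error rates additionally assume one result per eye, although each eye is read twice and 14.5 does not say how the reads combine. The documents do not support a claim that the planned model is shown to exceed its error rate, or that the choice of block is shown to reverse its conclusion. The point should be fixed before unmasking; it is not a reason to doubt the design.

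**What to change.** In section 14.5, make the subject the covariance block, holding all of that subject's eye-by-period records with an explicit covariance between right and left eyes. Alternatives are a subject random effect, or a subject-clustered variance with a small-sample correction. If a subject random effect is chosen, say how the population proportion of eyes is obtained, because back-transforming the fixed effects gives a proportion conditional on the random effect. In section 14.2, state whether 0.627 is a pass/fail or a logMAR correlation.

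The text change is about one sentence in each section and needs no extra subjects at about 40 completers. The statistical cost is a wider interval and some power, mainly where both eyes of one subject fail. As a rough guide, divide the eye count by 1.627 in the same stand-in. With 40 subjects, φ = 0.627 and a true proportion of 0.995, the permitted failures fall from 2 eyes to 1 and power falls from 97.7% to 87.3%, still above the planned 80%; the error at 0.90 falls from 3.8% to 1.3%. An unstructured block of four records has 4 × 5 / 2 = 10 covariance parameters, which may be hard to estimate with few failing eyes, so a simpler fallback structure should be named.
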